# 2.1 Hypothesis

- Hypothesis 1: Treatment for VIN II/III with ultrasonic aspiration will have a 60% reduction in recurrence rates over 12 months as compared to CO2 laser aspiration.
- Hypothesis 2: Treatment for VIN II/III with ultrasonic aspiration will demonstrate decreased incidence of pain and scarring up to 6 weeks following treatment as compared to CO2 laser aspiration.

Hypothesis 3: Treatment for VIN II/III with ultrasonic aspiration will demonstrate a decrease in change of sexual and psychosocial function (as demonstrated with validated instruments) in the 12 months following treatment as compared to CO2 laser aspiration.

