#### Secondary outcomes:

Secondary outcomes will compare:

1) Incidence of pain in the initial 7-10 days following treatment. Pain will be assessed using a patient pain scale. Participants will be asked to assess their own pain and report to the research team.

2) Incidence of scarring due to treatment regimen. Participants will be examined during regular post-procedure visit approximately 4-6 weeks following treatment. A visual exam of the vulva will be conducted to assess scaring.

3) Sexual function will be measured at baseline and at the 6 and 12 month follow-up visits. Changes in sexual function will be compared to baseline within each treatment arm. Overall sexual dysfunction rates will be compared between treatment arms for each study time interval. The Female Sexual Function (FSFI) and the Female Sexual Distraught Survey will be used to examine sexual function at each time point.

4) Wellness and Function will be measured using a validated instrument FACT-V health survey, designed specifically for women with vulva disease. The FACT-V provides metrics for functional, emotional, physical, and social well-being. Wellness and function scores will be compared between treatment arms for each study time interval and compared to baseline within each treatment arm.

Demographic and clinical data will also be collected in order to describe the study population and determine differences among the randomized groups. Demographic and clinical data will be verified against the participant medical records to assure data completion and minimize missing data in our analysis.

Demographic data will include: name, medical record number, contact information, date of birth, age, race/ethnicity, relationship status, and smoking status. Identifying information (name, medical record number, and contact information) will not be entered into the database by ancillary sites, and will only be used by research site to verify data, access medical records, and contact the patient for study visits. At these sites, a log will be kept with their identifiable data and participants will be linked to their study chart by study ID.

Clinical Data will include: menopause status, colposcopy results, treatment history, history of STDs, pre-existing medical conditions, concomitant medications, allergies, and vitals (blood pressure, pulse, temperature, respiratory rate, height, weight, BMI).

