## 6.2 Sample Size

Based on previous studies, approximately 37.5% of patients will reoccur within 12 months with traditional treatment (CO2 laser). [5, 7-13] We can detect a 60% reduction of recurrence to a rate of 15% at 80% power and an alpha of 0.05 with 62 patients per arm. [3] We will enroll an additional 13 patients per arm (n=75 per arm, 150 total) to account for noncompliance, lost to follow-up or misclassification diagnosis.

Approximately 75% of participants will be recruited at the coordinating site, University of Colorado Denver. The other 25% of participants will be recruited at the secondary sites Regional West Medical Center, and The University of Oklahoma are the secondary sites recruiting participants.

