All study treatment will be conducted by study-trained investigators only. The investigators chosen to participate in the study will all be board-certified gynecologists and will not include providers in-training. Gynecologists are trained to perform vulva sparing treatment in the clinical setting. All investigators elected for this study have a minimum of 3 years of clinical practice following fellowship. The coordinating site will host an in-service for all participating investigators prior to initiation of the study. The in-service will review the standard operating protocols of both devices. Ongoing monitoring and site visits by the PI will also be conducted to insure investigator compliance. In addition, secondary analysis will examine treatment differences per investigator.

Block randomization will be conducted using randomization statistical software. Research personnel will login into the study database and enter information for block randomization on the day of surgery. The randomization software associated with the REDCap data tool will provide the research team with the treatment assignment. Stratification variables will include multifocal disease and HPV status. The statistician responsible for statistical analysis will be blinded to the treatment received.

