## 14. Statistical Analysis

A per protocol analysis will be conducted. Participants receiving treatment per protocol will be included in the final analysis. Investigators will not have the option to change treatment assignment.

Descriptive statistics using means, frequencies, and percentages will be computed to describe the study population. Participant data will be analyzed employing the per protocol approach. Student's *t*-test (for continuous variables) and chi-square tests (for categorical variables) will be used to compare the two groups for demographic, and secondary outcome variables: pain, scarring, QOL scores. For the primary outcome measure rate of recurrence for each of the study endpoints, 3 months, 6 months and 12 months will be calculated per treatment arm and compared with initial bivariate analysis using chi-square analysis. Additional predictors for recurrence (pain, scarring, sexual function, and general wellness) will be compared similarly with chi-square for categorical variables and t-tests for continuous variables. Potential covariates (age, race, previous disease, etc.) will also be analyzed using bi-variate analysis. Variables found to be significant in the bivariate analysis will be included in multivariable analysis using logistic regression. Logistic regression models will be used to identify significant independent predictors associated with recurrence for each treatment arm. The logistic model will allow for control of study covariates. A p-value of <0.05 will be used to demonstrate statistical significance. IBM SPSS version 22 will be used for all statistical analyses.

Incidence of AEs and SAEs will be compared between treatment arms using chisquare analysis. A p-value of <0.05 will be used to demonstrate statistical significance.

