## 14.2 Secondary Endpoints

The secondary endpoints for this study are as follows:

Pain: Pain in the initial 7-10 days following treatment will be self-assessed using a pain scale. Average pain scores and incidence of high-level of pain will be determined for each treatment arm.

Scarring: Scarring in the 6 weeks following treatment will be assessed via visual exam by a study investigator. Incidence rates of scarring will be determined for each treatment arm.

Sexual function and sexual distraught: Sexual function and distraught will be assessed at baseline, 6, and 12 months following treatment. Mean scores for

function and distraught will be determined for each treatment arm per study time-point. Sexual function and distraught will be measured with validated instruments, The Female Sexual Function Index, and the Female Sexual Distress survey (Appendix 1.3 and 1.4).

Wellness and Function: General wellness and function will be assessed at baseline, 6, and 12 months following treatment. Mean scores for general function will be determined for each treatment arm per study time-point. Wellness will be measured using the validated instrument FACTS survey for vulvar malignancies (Appendix 1.2).

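### Hypothesis 3 is about a between-arm difference in change, but no baseline-adjusted between-arm test of FSFI, FSDS or FACT-V is stated, and women with early-detected recurrence have no 12-month score

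*Combined protocol and SAP*

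**What the plan says.** Section 2.1, Hypothesis 3, states that aspiration "will demonstrate a decrease in change of sexual and psychosocial function" over 12 months relative to laser. That is a comparison of change between arms.

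The analysis text is spread over three places.

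- **Section 4, Secondary outcomes.** For sexual function: "Changes in sexual function will be compared to baseline within each treatment arm", and "Overall sexual dysfunction rates will be compared between treatment arms for each study time interval". For FACT-V: "Wellness and function scores will be compared between treatment arms for each study time interval and compared to baseline within each treatment arm". Baseline enters only through the within-arm comparisons.
- **Section 14.** Student's t-test and chi-square tests "will be used to compare the two groups for demographic, and secondary outcome variables: pain, scarring, QOL scores". The only covariate-adjusted model in this section is a logistic regression with recurrence as its outcome.
- **Section 14.2.** FSFI and FSDS are summarised as mean scores by arm and time-point. For FACT-V: "Mean scores for general function will be determined for each treatment arm per study time-point".

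Randomization is stratified; section 7.1 says "Stratification variables will include multifocal disease and HPV status". Neither stratum appears in the analysis of these scores.

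On follow-up, sections 4 and 4.1 end a woman's participation at recurrence. Section 8 schedules the questionnaires at baseline, 6 months (V4) and 12 months (V5). Section 15.1.2 keeps data collected up to withdrawal but gives no missing-data method.

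**The concern.** One of the trial's three hypotheses has no stated test that matches it. The within-arm comparisons with baseline do not compare the treatments. The between-arm comparisons do not use the baseline score, although every woman is asked for it before treatment. Two things follow: available precision is given up, and a result that is significant in one arm but not in the other may be misread as a treatment difference.

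The second issue is who contributes at month 12. A woman whose recurrence is found before V5 is out of the study and gives no 12-month score. The comparison is then restricted by a post-treatment event that is also the primary outcome, and that the plan expects to differ between arms. The 6-month score is at less risk, because V4 includes the questionnaires and the score is lost only if recurrence is found before that visit. How often that would happen is unclear: sections 4 and 4.1 name a 3-month assessment that the visit list in section 8 does not contain. Section 11.2 also discontinues women after a serious adverse event. That is a further route to missing scores, though the same section knows of no such events after these procedures.

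**Working it through.** **Inputs from the plan.** Section 6.2: recurrence 37.5% (laser) and 15% (aspiration), "at 80% power and an alpha of 0.05 with 62 patients per arm", 75 per arm enrolled. Section 1.1: published recurrence of 25–50% (laser) and 22–35% (aspiration), with midpoints 37.5% and 28.5%.

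**Assumed, because the plan gives no value.** Two-sided alpha; baseline to follow-up correlation r = 0.3, 0.5, 0.7; share f of recurrences found before V5; score drop d of 0.5–1.0 SD after recurrence.

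**The plan's own figure.** No sample size is given for Hypothesis 3. The 62 is for recurrence. The pooled two-sided formula gives [1.96·√(2·0.2625·0.7375) + 0.842·√(0.375·0.625 + 0.15·0.85)]² / 0.225² = 59 per arm. With continuity correction it is 68. Power at 62 without correction is 82.1%. So 62 is not reproduced exactly; nothing below depends on that, and it serves only as the planned evaluable number.

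**Precision at 62 per arm.** The two-sample t-test at 80% power detects 0.507 SD. Baseline adjustment multiplies this by √(1 − r²).

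| r | √(1 − r²) | Detectable difference (SD) | Power for 0.4 SD |
|---|---|---|---|
| unadjusted | 1 | 0.507 | 60% |
| 0.3 | 0.954 | 0.484 | 64% |
| 0.5 | 0.866 | 0.439 | 72% |
| 0.7 | 0.714 | 0.362 | 87% |

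At r = 0.5 this is worth 62 / (1 − 0.25) ≈ 83 unadjusted women per arm. The figures apply to mean scores, not to dysfunction rates.

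**Separate within-arm tests.** If both arms truly change by the same amount and each test has power π, exactly one arm is significant with probability 2π(1 − π): 50% at π = 0.5 and 32% at π = 0.8.

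**Missing 12-month scores.** The expected proportion is f·p. At f = 0.5 this is 0.1875 and 0.075: 14.1 and 5.6 of 75, or 11.6 and 4.6 of 62. That leaves about 50 and 57 of 62, where the unadjusted detectable difference is 0.55 SD. At f = 1, an upper bound, it is 28.1 and 11.2 of 75.

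**Selection bias at month 12.** Among women still observed, the proportion with recurrence is q = (1 − f)p / (1 − f·p). With scores scaled so that higher is better, and L and A for laser and aspiration, bias = (d_L·q_L − d_A·q_A) − (d_L·p_L − d_A·p_A). Positive values favour aspiration.

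Example at f = 0.5, d = 1: q_L = 0.1875/0.8125 = 0.231 and q_A = 0.075/0.925 = 0.081, so bias = 0.150 − 0.225 = −0.075.

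| Recurrence L v A | f, L v A | d, L v A (SD) | Bias (SD) |
|---|---|---|---|
| 37.5% v 15% | 0.5 both | 0.5; 1.0 both | −0.038; −0.075 |
| 37.5% v 15% | 1 both (upper bound) | 0.5; 1.0 both | −0.113; −0.225 |
| 37.5% v 28.5% | 0.5 both | 0.5; 1.0 both | −0.013; −0.025 |
| 37.5% both | 0.5 v 0.75 | 1.0 both | +0.100 |
| 37.5% v 28.5% | 0.5 v 0.75 | 1.0 both | +0.050 |
| 37.5% both | 0.75 v 0.5 | 1.0 both | −0.100 |
| 37.5% v 28.5% | 0.75 v 0.5 | 1.0 both | −0.126 |
| 37.5% both | 0.5 both | 0.5 v 1.0, or reversed | +0.072 or −0.072 |

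The bias is zero if recurrence, timing and drop are all equal between arms, or if recurrence leaves the score unchanged.

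**The case against.** Under 1:1 randomization with complete data, the expected difference in follow-up scores equals the expected difference in change. The planned t-test therefore addresses Hypothesis 3 without bias, and section 4's reference to time intervals can be read as covering change. The correlations are assumed, and at r = 0.3 the gain is small. Section 4 puts a between-arm comparison beside each within-arm one, so misreading is a risk rather than the plan. The selection bias rests on assumed inputs; with equal timing and half found early it is small beside a detectable 0.51–0.55 SD and works against aspiration. Both arms share one visit schedule, so unequal timing has no basis in the documents. Finally, calling it bias presumes that scores after recurrence belong in the target, which the plan does not say.

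Most of this stands as a limit on size. It does not remove the point. Even if intervals mean change, no adjustment for baseline or strata is stated, and the precision it offers is free. The size and sign of the month-12 bias are uncertain precisely because those scores would not be collected. The plan does not say how recurrence is to be handled for these scores, and that choice has to be made before the data are lost.

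**Conclusion.** The concern holds as a secondary-outcome issue that should be fixed. The main part is a mismatch between Hypothesis 3 and the stated tests. It costs precision rather than validity: 0.51 SD detectable as planned against 0.48 to 0.36 SD with baseline adjustment, for r from 0.3 to 0.7.

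The secondary part is the possible bias at month 12. At the planning rates, with equal timing and drop and half of recurrences found early, an aspiration advantage is understated by 0.04–0.075 SD, or by 0.013–0.025 SD at the section 1.1 midpoints. The direction is not assured, since unequal timing or drop can move the difference either way even when recurrence is equal. Confidence is medium, because the correlation, detection share and score drop are all assumptions.

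**What to change.** **Analysis (sections 14 and 14.2).** Make the between-arm test of each FSFI, FSDS and FACT-V score an ANCOVA or a repeated-measures mixed model at 6 and 12 months, with baseline score, HPV status and multifocal status as covariates. Name one of the two in advance, since they can treat women with only one follow-up score differently. For dysfunction rates, use logistic regression with the same covariates and report adjusted rates, so that the target remains the rate comparison in section 4; the definition of dysfunction must also be stated, because no cut-off is given. Label the within-arm comparisons descriptive. This costs nothing in data: baseline scores and strata are already collected. If r is only 0.3, the gain is small.

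**Follow-up (sections 4 and 4.1).** Keep sending the 6- and 12-month questionnaires after recurrence, electronically or by phone as at V2, with no change to clinical care. State that this is a treatment-policy comparison, and report the analysis restricted to women without recurrence as a sensitivity analysis. It needs a short protocol and consent wording change and, with half of recurrences found early, about 14 laser and 6 aspiration women surveyed remotely at month 12 (at most 28 and 11). The drawback is that scores after recurrence also reflect re-treatment, so the contrast is no longer of the index procedure alone.

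Both changes work within the per-protocol population of sections 9 and 14. Whether to analyse these scores as randomized is a separate decision and should be stated separately.

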#### 4.1. Study Endpoints

Patients will be enrolled at participating centers prior to receiving treatment for their VIN II/III. Baseline assessments will include all study surveys and collection of demographic and clinical data.

Pain and scarring will be assessed within the first 6 weeks following treatment. Participants will be followed at 3, 6, and 12 months for recurrence. Participants will be discontinued from the study at time of recurrence, or at the completion of 12 months follow-up. Total participation is 12 months duration.

## 5. Ethical Considerations

## 5.1 Good Clinical Practice

This study will be conducted in accordance with Good Clinical Practice (GCP), as defined by the International Conference on Harmonisation (ICH) and in accordance with the ethical principles underlying European Union Directive 2001/20/EC and the United States Code of Federal Regulations, Title 21, Part 50 (21CFR50).

The study will be conducted in compliance with the protocol. The protocol, any amendments, and the subject informed consent will receive Institutional Review Board (IRB) approval before initiation of the study.

All potential serious breaches must be reported to The University of Colorado IRB immediately. A serious breach is a breach of the conditions and principles of GCP in connection with the study or the protocol, which is likely to affect, to a significant degree, the safety or physical or mental integrity of the subjects of the study or the scientific value of the study.

Study personnel involved in conducting this study will be qualified by education, training, and experience to perform their respective tasks.

This study will not use the services of study personnel where sanctions have been invoked or where there has been scientific misconduct or fraud (e.g., loss of medical licensure; debarment).

# 5.2 Institutional Review Board

Before study initiation, the investigator will have written and dated approval from COMIRB for the protocol, consent form, subject recruitment process, and any other written information to be provided to subjects.

The investigator will provide COMIRB with continuing review reports annually. In addition, any revised study materials or amendments will be submitted for approval prior to use/implementation.

Each additional site will obtain local IRB approval prior to any procedures being conducted. The University of Colorado Denver study team will provide study monitoring and will audit study sites, requiring direct access to source data and documents. The study will remain open with each site's local IRB until receipt of notification from coordinating site to close the study. All correspondence with the local IRB will be maintained in the study regulatory files. The sponsor may request additional audit of study sites.

## 5.3 Informed Consent

Potential Participants will be approached for participation at their initial visit in our gynecologic clinics. Investigators will ensure that subjects are clearly and fully informed about the purpose, potential risks, and other critical issues regarding clinical studies in which they volunteer to participate.

Investigators will:

1) Provide a copy of the consent form and written information about the study prior to clinical study participation. The language will be non-technical and easily understood.

- 2) Allow time necessary for subject to inquire about the details of the study.
- 3) Obtain an informed consent signed and personally dated by the participant and by the person who conducted the informed consent discussion.
- 4) Obtain IRB approval of the written informed consent form and any other information to be provided to the subjects, prior to the beginning of the study, and after any revisions are completed for new information.
- 5) Revise the informed consent whenever important new information becomes available that is relevant to the participant's consent. The investigator, or a person designated by the investigator, will fully inform the subject of all pertinent aspects of the study and of any new information relevant to the participant's willingness to continue participation in the study. This communication will be documented.

The rights, safety, and well-being of the study participants are the most important considerations and will prevail over interests of science and society.

# 6. Investigational Plan

## 6.1 Description of Population to be Enrolled

Women diagnosed with high-grade vulvar intraepithelial neoplasia (VIN II/III) will be eligible to participate. Women with prior treatment for dysplasia will be considered eligible for the study. Prior treatment for dysplasia includes all treatments such as surgery, laser ablation, and/or aldara (a topical agent).

## 6.1.1. Inclusion Criteria:

- Women 18-89 years old
- Diagnosed with VIN II/III (diagnosed by pathology)
- Referred for vulva sparing treatment for dysplasia
- Available for follow-up of treatment for 12 months

## 6.1.2 Exclusion Criteria:

- Women who are pregnant
- Women with VIN I dysplasia (diagnosed by pathology)
- Women with vaginal intraepithelial neoplasia (VAIN)
- Women requiring vulvectomy for treatment
- Women unable to provide informed consent

Women with suspected dysplasia will undergo routine biopsy for diagnosis of vulva dysplasia. Pathology will categorize disease as either "low-grade" or "high-grade" or using the grading I, II, and III. Women with high-grade dysplasia, VIN II/III, will be referred for further treatment. Women meeting the inclusion criteria will be eligible for inclusion. Women with low-grade dysplasia, VIN I, will not be included in the study.

## 6.2 Sample Size

Based on previous studies, approximately 37.5% of patients will reoccur within 12 months with traditional treatment (CO2 laser). [5, 7-13] We can detect a 60% reduction of recurrence to a rate of 15% at 80% power and an alpha of 0.05 with 62 patients per arm. [3] We will enroll an additional 13 patients per arm (n=75 per arm, 150 total) to account for noncompliance, lost to follow-up or misclassification diagnosis.

Approximately 75% of participants will be recruited at the coordinating site, University of Colorado Denver. The other 25% of participants will be recruited at the secondary sites Regional West Medical Center, and The University of Oklahoma are the secondary sites recruiting participants.

